6.4.2. Exposure for Pembrolizumab

Exposure for pembrolizumab will be summarized as follows:

- **Total number of infusions:** Total number of infusions per subject with a nonzero dose of pembrolizumab.
- **Total dose administered (mg):** Sum of the cumulative dose of pembrolizumab that has been administered.

For an infusion i , let C_i be the concentration (mg/mL) of pembrolizumab and V_i be the total volume administered (in mL) reported on the pembrolizumab dosing eCRF; let N be the total number of infusions

$$\text{Total dose administered (mg)} = \sum_{i=1}^N C_i \times V_i$$

- **Duration of treatment (days):** Date of last dose of pembrolizumab – date of first dose of pembrolizumab + 1.

6.4.3. Exposure for Azacitidine

Exposure for azacitidine will be summarized as follows:

- **Total number of administrations:** Total number of infusions and injections per subject with a nonzero dose of azacitidine.
- **Total dose administered (mg):** Sum of the cumulative dose of azacitidine that has been administered.

For an infusion/injection i , let C_i be the concentration (mg/mL) of azacitidine and V_i be the total volume administered (mL) reported on the azacitidine dosing eCRF if the i th administration is through IV; let M_i be the actual dose administered (mg) if the i th administration is through SC. Let

$$I_{IV,i} = \begin{cases} 1, & \text{administered through IV} \\ 0, & \text{administered through SC} \end{cases}$$

$$I_{SC,i} = \begin{cases} 1, & \text{administered through SC} \\ 0, & \text{administered through IV} \end{cases}$$

Suppose N is the total number of infusions and injections,

$$\text{Total dose administered (mg)} = \sum_{i=1}^N (C_i \times V_i \times I_{IV,i} + M_i \times I_{SC,i})$$

- **Average dose (mg):** Total dose administered (mg) / total number of injections and infusions.
- **Duration of treatment (days):** Date of last dose of azacitidine – date of first dose of azacitidine + 1.

6.5. Study Drug Compliance

For subjects in the safety population, overall compliance (%) for epacadostat will be calculated for all subjects as

$$\text{Compliance (\%)} = 100 \times [\text{total dose actually taken}] / [\text{total prescribed dose}].$$

The total prescribed dose is defined as the sum of the doses prescribed by the investigator accounting for dose modifications.

The total actual dose taken will be calculated based on information entered on the drug accountability eCRF. If there is dispensed drug that has not been returned yet, this dispensed drug kit will not be considered.

Compliance calculations are not necessary for IV or SC administered agents (eg, pembrolizumab and azacitidine).

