4.5. Overall Study Duration

The study begins when the first subject signs the ICF. The end of the study will occur when all subjects have discontinued the study and the last follow-up visit has been performed.

If there have been 5 subjects on study for more than 6 months, a database lock of the study may occur to allow the analysis of the study data. Any remaining subjects may continue to receive study treatment and be seen by the investigator per protocol. The investigator will be expected to monitor for and report any SAEs, AEs of special interest, and pregnancies, as detailed in Section 8. The remaining subjects are considered to be on study until a discontinuation criterion is met and written notification is provided to the sponsor.

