5.2. Study Drugs

5.2.1. Epacadostat

5.2.1.1. Description and Administration

Epacadostat will be available as 25 or 100 mg tablets to be administered in a BID administration schedule. All BID doses of epacadostat will be taken PO in the morning and evening, approximately 12 hours apart without regard to food. If the morning or evening dose is missed by more than 4 hours, then that dose should be skipped, and the next scheduled dose should be taken at the usual time. Doses of epacadostat will be self-administered except on the days scheduled to be given at the study clinic (see Section 6).

Subjects should be counseled by the investigator to maintain strict adherence to the study regimen as prescribed and to keep a record of any missed doses. The subject will be instructed to bring all unopened, empty, and opened/partially used bottles of study drug at Day 1 study visits, at which time compliance will be assessed.

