4.2.5. Cycle Length and Duration

For Treatment Group A, Cycle 1 Day 1 is the day that the first dose of pembrolizumab is administered. Scheduled cycle length is 21 days. Actual Day 1 of subsequent cycles will correspond with the first day of administration of pembrolizumab for Treatment Group A in that cycle; thus, treatment cycles may become out of sync with the originally planned schedule, and cycle length may be different from 21 days (\pm 3-day window for subsequent cycles). The date of Day 1 of subsequent cycles recorded on the eCRF will be used as Day 1 of the subsequent cycles.

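### SAP 6.5 writes the unreturned-kit exclusion into epacadostat dose taken but not into prescribed dose, so read literally it understates compliance for any subject with an outstanding kit

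*SAP*

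**What the plan says.** SAP 6.5 defines one compliance measure, for epacadostat only: "overall compliance (%) for epacadostat will be calculated for all subjects as" 100 times the total dose taken divided by the total prescribed dose. Intravenous and subcutaneous agents are exempt.

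Each term has its own paragraph.
- **Denominator:** "The total prescribed dose is defined as the sum of the doses prescribed by the investigator accounting for dose modifications".
- **Numerator:** "The total actual dose taken will be calculated based on information entered on the drug accountability eCRF". The next sentence, in the same paragraph, is the unreturned-kit rule: "If there is dispensed drug that has not been returned yet, this dispensed drug kit will not be considered".

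No matching rule is written for the denominator, and the section does not cover a subject with no returned kit.

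On returns, Protocol 5.2.1.1 states: "The subject will be instructed to bring all unopened, empty, and opened/partially used bottles of study drug at Day 1 study visits". Protocol 4.5 allows a database lock while some subjects are still on treatment: "Any remaining subjects may continue to receive study treatment and be seen by the investigator per protocol".

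The result feeds Table 3.1.2.1 (flagged as an in-text table) and Listing 2.5 in SAP Appendix A.

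**The concern.** A compliance ratio is interpretable only if both terms cover the same treatment time. Here one term depends on bottle returns and the other on prescriptions, and only the first has an exclusion. A programmer who follows the two definitions as written removes the tablets in an outstanding kit from dose taken but leaves the days they covered in prescribed dose. A second programmer could take the kit out of the whole calculation, and the same data would then give a different table.

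Outstanding kits are foreseeable. The SAP rule itself anticipates them, and because bottles come back at Day 1 visits, a subject in mid-cycle normally holds an open one. At stake is the only compliance percentage that the trial reports.

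**Working it through.** **No figure to reproduce.** The plan states no compliance value, target or threshold. The check is therefore the direct consequence of the two definitions.

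**Inputs**
- Twice-daily dosing: "Epacadostat will be available as 25 or 100 mg tablets to be administered in a BID administration schedule" (Protocol 5.2.1.1).
- Cycle: "Scheduled cycle length is 21 days" (SAP 4.2.5).
- Planned doses per cycle: 2 × 21 = 42. As a check, 0.75 × 42 = 31.5, which rounds up to 32, the epacadostat count in the 75% DLT-evaluability rule (SAP 3.1.2).
- Kit size: not in the documents. Assumption: one kit is one 21-day supply.
- Adherence: assumed complete, so the correct answer is 100%.

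**Literal reading.** Let k be the number of cycles prescribed, with the last kit fully used but outstanding, and D the dose per cycle.

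Compliance = 100 × (k − 1)D / (kD) = 100 × (k − 1)/k

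D cancels, so the result is the same at 100 mg and 300 mg BID. For example, at 100 mg BID, D = 100 × 42 = 4,200 mg, and k = 3 gives 8,400 / 12,600 = 66.7%.

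| Cycles k | Literal reading | Kit removed from both terms |
|---|---|---|
| 1 | 0% | not calculable (0/0) |
| 2 | 50.0% | 100% |
| 3 | 66.7% | 100% |
| 6 | 83.3% | 100% |
| 8 | 87.5% | 100% |
| 12 | 91.7% | 100% |
| 35 | 97.1% | 100% |

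The shortfall is 1/k. Literal compliance reaches 90% from 10 cycles and 95% from 20.

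**Partly used kit.** With c completed cycles and a data cut d days into the current kit, compliance = 100 × 21c / (21c + d).
- c = 2: 42/49 = 85.7% at 7 days, 42/56 = 75.0% at 14, 42/63 = 66.7% at 21.
- c = 8: 168/175 = 96.0%, 168/182 = 92.3%, 168/189 = 88.9%.

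**Smaller kits.** If a cycle's supply is m equal kits and one is outstanding, the shortfall is 1/(mk). With m = 2 (an assumption), 3 cycles gives 100 × (1 − 1/6) = 83.3%, and 8 cycles gives 100 × (1 − 1/16) = 93.8%.

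**Incomplete adherence.** A subject who takes 80% of tablets would show 0.8 × 2/3 = 53.3% at 3 cycles and 0.8 × 7/8 = 70.0% at 8. With matched terms the figure is 80% in both cases.

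**Effect on a group mean.** SAP 5.2 summarises data by dose level, and SAP 3.4.1.1 gives 3 to 9 subjects per escalation level. In an illustrative group of six fully adherent subjects, one affected 2-cycle subject lowers the mean to (5 × 100 + 50)/6 = 91.7%. Dose levels that also include Part 2 subjects would be diluted further.

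**The case against.** The best defence is textual. The rule says that the kit is not considered; it does not say that only the dose taken is reduced. A reader might infer that the SAP deliberately keeps the outstanding days in the prescribed dose. It does not say so. That follows from its silence, and on the matched reading the error is zero for any subject with at least one returned kit. This part stands, so the understatement belongs to the literal reading. But nothing in 6.5 tells a programmer to remove those days or how to identify them, and the matched reading leaves 0/0 unaddressed.

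A reader might also infer that fully adherent subjects will be reported as markedly non-compliant. The SAP defines no cut-off, and the shortfall is large only on short treatment. The subjects left on drug under Protocol 4.5 do not supply the 50% and 67% cases: that provision is framed around a few subjects on study for more than 6 months, roughly 8 cycles or more, where the shortfall is about 12.5 points or less.

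Nor do the documents support reading the ratio as a site effect or as the trial's evidence on tolerability. No by-site compliance output is planned. SAP 6.4.1 reports treatment duration and average daily dose, and SAP 8.2.5 reports interruptions, reductions and discontinuations due to adverse events.

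Finally, procedures limit the problem. Protocol 5.3 requires tablet counts with sponsor monitoring, the schedules assess compliance through end of treatment, and Protocol 10.2 has sites record returns and keep containers until verified. These reduce the number of outstanding kits. They do not change what happens to one that remains outstanding.

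**Conclusion.** The point holds as a mismatch in the written definitions. Following SAP 6.5 literally gives a ratio whose terms cover different periods and understates compliance whenever an epacadostat kit is outstanding. The shortfall is 1/k under one fully used kit per cycle: 33 points at 3 cycles, 12.5 at 8 and 2.9 at 35, and less with partly used or smaller kits. These sizes rest on the assumed kit content and on the literal reading.

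The consequence is limited to descriptive Table 3.1.2.1 and Listing 2.5. Neither analysis population in SAP 5.3 uses the ratio, and the 75% DLT rule is based on doses received. The share of subjects affected cannot be determined from the documents. The text should be corrected before the table is programmed, but no efficacy or safety conclusion depends on it.

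**What to change.** Replace the unreturned-kit sentence in SAP 6.5 with wording such as: dose taken and prescribed dose are both restricted to dispensing periods whose kits have been returned; a period with an unreturned kit is left out of both terms; compliance is missing, not 0%, if no kit was returned. Add to Table 3.1.2.1 the number of subjects with at least one excluded period.

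The cost is a short SAP edit and a small programming change. The sponsor should first confirm that dispensing and return dates are available, because the accountability eCRF is not among the documents. SAP 6.4.1 does not name the source of the epacadostat total dose, so it is worth checking at the same time that average daily dose does not rely on the same returns.

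The downside is that compliance covers slightly less treatment time in subjects with an excluded period.

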6.6. Prior and Concomitant Medication

For subjects in the safety population, prior medications and concomitant medications will be coded using the WHO Drug Dictionary and summarized by WHO drug class and WHO drug term. Results will be summarized as number and percentage of subjects with prior and concomitant medications by PT and WHO drug class.

7. EFFICACY

A list of planned tables and listings is provided in [Appendix A](#).

7.1. General Considerations

Efficacy endpoints of this study include ORR, DOR, PFS and OS by investigator assessment based on RECIST v1.1. Listings of response assessment at each visit will be provided.

7.2. Analysis of the Efficacy Parameters

7.2.1. Response Criteria

Overall disease status will be categorized using RECIST v1.1. Subjects will have their overall response evaluated as CR, PR, SD, PD, or NE at each postbaseline radiological assessment based on changes in target lesions, nontarget lesions, and appearance of new lesions.

7.2.2. Objective Response Rates and Best Overall Response

A subject is defined as an objective responder if the subject has an overall response of CR or PR at any postbaseline visit prior to first PD. Objective responders will be assessed based on RECIST v1.1.

Objective response rate is defined as the proportion of subjects with objective responses. Objective response rate will be estimated with 95% CIs overall by cohort-specific tumor type. CIs will be calculated based on the method for Simon 2-stage CIs of response rates outlined in Koyama and Chen (2008). Subjects who do not have sufficient baseline data to ascertain response will be included in the denominators in the calculation of ORR.

In general, the best response is determined on subject level using the highest overall response achieved postbaseline prior to and including the first PD, in the order of CR, PR, SD, PD, and NE. Responses of CR, PR, or SD after a response of PD will not be considered in determining best response by RECIST v1.1 criteria. In the case of SD, measurements must meet the SD criteria at least after the date of first dose at a minimum of 56 days (9 weeks – 7-day window). Subjects who fail to meet this criterion will have best overall response of PD if the next available assessment indicated PD, or NE if there is no additional assessment available.

Under RECIST v1.1, the best response is determined by subject using the highest overall response achieved postbaseline prior to and including the first PD, in the order of CR, PR, SD, PD, and NE. Responses of CR, PR, or SD after a response of PD will not be considered in determining best response by RECIST v1.1 criteria. In the case of SD, measurements must meet the SD criteria at least after the date of first dose of study drug at a minimum of 56 days (9 weeks – 7-day window). Subjects who fail to meet this criterion will have best overall

response of PD if the next available assessment indicated PD, or NE if there is no additional assessment available.

For subjects with measurable disease at baseline, the RECIST v1.1 assessment criteria presented in [Table 11](#) can be used to determine the overall disease status at a given time point based on the target lesion, nontarget lesion, and new lesion assessment.

Table 11: RECIST Evaluation Criteria for Overall Response: Measurable Disease at Baseline

Target Lesions	Nontarget Lesions	New Lesions	Overall Response
CR	CR	No	CR
CR	Non-CR/Non-PD	No	PR
CR	NE	No	PR
PR	Non-PD or NE	No	PR
SD	Non-PD or NE	No	SD
Not all evaluated	Non-PD	No	NE
PD	Any	Yes or No	PD
Any	PD	Yes or No	PD
Any	Any	Yes	PD

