5.6.3. Prohibited Medications

Subjects are prohibited from receiving the following therapies during the screening and treatment phase of this study unless otherwise noted below:

- Any investigational medication other than the study drugs.
- Any anticancer medications, including chemotherapy or biologic therapy other than the study medications.
- Any immunological-based treatment for any reason. (NOTE: Completed adjuvant therapy [eg. vaccines] is permitted with medical monitor approval). Inhaled or topical steroids are allowed, and systemic steroids at doses 10 mg/day prednisone or equivalents are allowed with medical monitor approval, as described in Section 5.6.2, and immune suppressants are allowed for treatment for immune toxicities.)
- Radiation therapy.

NOTE: Radiation therapy to a symptomatic solitary lesion or to the brain may be allowed after consultation with the sponsor's medical monitor.

- Live vaccines within 30 days before the first dose of study treatment and while participating in the study. Examples of live vaccines include, but are not limited to, the following: measles, mumps, mumps, chicken pox, yellow fever, rabies, Bacillus Calmette-Guerin, and typhoid vaccine. Seasonal influenza vaccines for injection are generally killed virus vaccines and are allowed; however, intranasal influenza vaccines (eg. FluMist) are live attenuated vaccines and are not allowed.

- Any MAOI or drug associated with significant MAO inhibitory activity agents is prohibited from 21 days before Day 1 through 2 weeks after the final dose of epacadostat has been taken (see [Appendix C](#)).
- Any UGT1A9 inhibitor, including acitretin, amitriptyline, androsterone, cyclosporine, dasatinib, diclofenac, diflunisal, efavirenz, erlotinib, estradiol (17-beta), flutamide, gefitinib, gemfibrozil, glycylnetic acid, glycylnhizin, imatinib, imipramine, ketoconazole, linoleic acid, mefenamic acid, mycophenolic acid, niflumic acid, nilotinib, phenobarbital, phenylbutazone, phenytoin, probenecid, quinidine, ritonavir, Sorafenib, sulfapyrazone, valproic acid, and verapamil.
- Treatment Group B only: Use of coumarin-based anticoagulants (eg, Coumadin) is prohibited. Investigators are encouraged to switch subjects to alternate anticoagulation therapies such as Eliquis®, Pradaxa®, Savaysa®, or Xarelto®. Coagulation panel should be monitored more closely while a subject is on any anticoagulant.

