Subjects who, in the assessment by the investigator, require the use of any of the aforementioned treatments for clinical management should be removed from the study. Subjects may receive other medications that the investigator deems to be medically necessary.

6_ STUDY ASSESSMENTS

All study assessments will be performed as indicated in the schedule of assessments ([Table 29](#), [Table 31](#), [Table 33](#), [Table 35](#), [Table 37](#), [Table 39](#), [Table 41](#), [Table 43](#), [Table 45](#), and [Table 47](#)), and all laboratory assessments will be performed as indicated in [Table 30](#), [Table 32](#), [Table 34](#), [Table 36](#), [Table 38](#), [Table 40](#), [Table 42](#), [Table 44](#), [Table 46](#), and [Table 48](#).

[Table 49](#) presents a summary of clinical laboratory analytes to be assessed. The order of assessments is suggested by the order of mention within the schedule. See [Section 7](#) for instructions on each assessment. Further details of study procedures and assessments can be found in the study reference manual.

Table 29: Schedule of Assessments (Treatment Group A: Part 1 and Part 2 Expansion Cohorts A-1 and A-2)

Visit Day	Screening	Treatment							EOT	Safety Follow-Up	Notes
		CI DI	CI DS-7	CI DIS	C2 DI	C2 DS-7	C2 DIS	C3+ DI			
Evaluation Window	Day -28 to Day-I	DI	DS-7	± 3d	± 3d	DS-7	±3 d	±3 d	+S d	EOT + 42-49 d	
ADMINISTRATIVE PROCEDURES											
Informed consent	X										
Contact iRT	X	X			X			X	X		
Inclusion/exclusion criteria	X	X									
Medical and cancer history	X										
Prior/concomitant medications	X	X	X*	X	X	X*	X**	X	X	X	* Visit to occur on the fifth day of azacitidine dose administration. ** Cycle 2 Day 15 visits are not required for subjects in Part 2.
Distribute reminder cards	X	X	X*	X	X	X*	X**	X	X		* Visit to occur on the fifth day of azacitidine dose administration. ** Cycle 2 Day 15 visits are not required for subjects in Part 2.
Study drug dispensing		X			X			X			
Assess study drug compliance					X			X	X		
CLINICAL PROCEDURES AND ASSESSMENTS											
Physical examination/body weight and height*	X	X	X**	X	X	X**	X***	X	X	X	* Comprehensive examination at screening, targeted physical examination thereafter. Height at screening only. ** Visit to occur on the fifth day of azacitidine dose administration. *** Cycle 2 Day 15 visits are not required for subjects in Part 2.

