7.2.5. Progression-Free Survival

Progression-free survival will be assessed by RECIST v1.1.

[figure not shown]
Censoring for PFS will follow the algorithm outlined in [Table 12](#), which is based on the FDA Guidance for Industry: Clinical Trial Endpoints for the Approval of Cancer Drugs and Biologics ([FDA 2007](#)).

The KM estimate of median PFS will be presented with its 95% CI. The 95% CI will be calculated using Brookmeyer and Crowley's method (1982).

Table 12: Evaluation and Censoring of Progression-Free Survival

Situation	Outcome	Date of Progression or Censoring
No baseline tumor assessments	Censored	Date of Day 1
No valid postbaseline response assessments	Censored	Date of Day 1
Progression documented between scheduled response assessments	Progressed	Date of first overall response of PD
No progression	Censored	Date of last valid radiologic assessment (not NE and not missing)
Study discontinuation for undocumented progression	Censored	Date of last valid radiologic assessment (not NE and not missing)
Study discontinuation for toxicity or other reason	Censored	Date of last valid radiologic assessment (not NE and not missing)
New anticancer treatment started	Censored	Date of last valid radiologic assessment (not NE and not missing) on/before starting a new anticancer treatment.
Death before first progressive response assessment	Progressed	Date of death
Death between adequate response assessments	Progressed	Date of death
Death or progression after more than 1 missed assessment	Censored	Date of last valid radiologic assessment (not NE and not missing) prior to death

Under RECIST v1.1, PFS is defined as the length of time between the baseline visit (Day 1) and the earlier of death or first assessment of PD. Date of death will be determined using the Death Report, Survival Follow-Up, and Subject Status eCRFs.

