10.1. Changes to Protocol-Defined Analyses

10.1.1. Efficacy Analyses

- The efficacy endpoints will only be summarized per RECIST v1.1. [REDACTED]
- The confirmation of responses will not be included.

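### The ORR response window in SAP 7.2.2 closes only at first PD, so a response produced by permitted on-study radiotherapy to a target lesion would be credited to the study drugs

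*SAP*

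**What the plan says.** **Response.** SAP 7.2.2 defines an "objective responder if the subject has an overall response of CR or PR at any postbaseline visit prior to first PD". Best overall response has the same limit: "Responses of CR, PR, or SD after a response of PD will not be considered in determining best response by RECIST v1.1 criteria". Neither rule mentions radiotherapy or a new anticancer therapy. SAP 10.1.1 adds: "The confirmation of responses will not be included". One qualifying scan is therefore enough. SAP 7.2.4 takes the largest decrease in target-lesion size and sets no date after which scans stop counting.

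**Radiotherapy.** Protocol 5.6.3 lists radiation among the prohibited therapies, with an exception: "Radiation therapy to a symptomatic solitary lesion or to the brain may be allowed after consultation with the sponsor's medical monitor". The section closes by saying that subjects who, in the investigator's assessment, "require the use of any of the aforementioned treatments for clinical management should be removed from the study".

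**PFS and DOR.** SAP Table 12 censors PFS when a new anticancer treatment starts, at the "Date of last valid radiologic assessment (not NE and not missing) on/before starting a new anticancer treatment". SAP 7.2.3 applies the same algorithm to DOR. The SAP does not say whether on-study radiotherapy is a new anticancer treatment.

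**The concern.** ORR is the primary Part 2 endpoint and is meant to describe the activity of the drug combination. Local radiation can shrink the lesion it is aimed at. If a subject is irradiated under the exception, stays on study and is scanned again before progression, the stated rule has no means of keeping that shrinkage out of ORR, best overall response or best percent change. The two secondary time-to-event endpoints are cut off at new anticancer treatment and the primary endpoint is not. In small cohorts with a low reference rate, one such subject visibly moves the estimate.

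**Working it through.** **1. The plan's own figures.** Inputs from SAP Table 10: p0 = 3%, p1 = 20%, n1 = 8, n2 = 19, n = 27, r1 = 0, r = 2.
- Early termination: (1 − p)^8 gives 0.97^8 = 0.7837 and 0.80^8 = 0.1678, matching Protocol 9.6.
- Rejection: the sum over x1 = 1 to 8 of P(X1 = x1) × P(X2 ≥ 3 − x1), with X1 from 8 and X2 from 19 subjects, gives 0.0319 at 3% and 0.8002 at 20%, consistent with the stated 0.05 and 80%.

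The design is sound. The point concerns which scans may produce a response and changes none of these figures.

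**2. What has to happen for a miscounted response.**
- Radiation is given under the 5.6.3 exception and the subject remains on study.
- The irradiated lesion is a target lesion. Protocol 7.6.1.1 advises against choosing previously irradiated lesions as targets, but that applies at baseline. No visible text changes a lesion's status after on-study radiation.
- Under SAP Table 11, the target assessment reaches PR or CR, nontarget lesions are not PD, and there is no new lesion.
- This is seen on a scan before first PD. Scans run every 9 weeks (Protocol 7.6.1.2).

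All four can occur within the protocol. Brain radiation, or radiation to a nontarget lesion, would seldom meet the second and third conditions.

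**3. Two readings of on-study radiotherapy.**
- *It is not new anticancer treatment.* Imaging continues, SAP 7.2.2 counts the later response, and Table 12 does not cut PFS or DOR. This is the live gap.
- *It is new anticancer treatment.* Protocol 7.6.1.2 ends imaging at that point. Only a scan taken outside the protocol could show a later response. If one were taken, 7.2.2 would count it, while the DOR censoring date would precede the response.

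**4. Size on the ORR scale.** The documents give no frequency of on-study irradiation.
- One case in 8: 1/8 = 12.5 points.
- One case in 27: 1/27 = 3.7 points, for example 2/27 = 7.4% becoming 3/27 = 11.1%.

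These are planned cohort sizes; enrollment stopped early. As an assumption, let f be the share of true non-responders miscounted. A true ORR of 3% would then be estimated around 0.03 + 0.97f:

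| f (assumed) | Expected ORR |
|---|---|
| 0% | 3.00% |
| 1% | 3.97% |
| 2% | 4.94% |
| 3% | 5.91% |
| 5% | 7.85% |

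**The case against.** **Conduct rules cover much of this.** Other anticancer drugs are prohibited, subjects who need prohibited treatment should leave the study, and imaging ends at new anticancer treatment. This stands for new systemic therapy, where few later scans should exist. It does not settle radiotherapy: if the removal sentence also covered radiation allowed under the exception, the exception would have no use.

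**A rule may exist elsewhere.** The body of Protocol 7.6.1, on disease assessment, is not in the public text, so a lesion-level rule there cannot be excluded. This stands as a limit. The SAP refers to no such rule.

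**The route is narrow.** The exception needs consultation, response is by investigator assessment, and Table 11 allows a not-evaluable result. The protocol also accepts previously irradiated lesions as measurable when they have progressed (Protocol 3.1), so its baseline caution is not absolute. All this points to few cases.

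**Stronger readings that the documents do not support.**
- A reader might infer that any shrinkage of an irradiated lesion counts as a response. It counts only if the Table 11 conditions are met.
- A reader might infer that the rules routinely yield negative durations of response. That needs an off-protocol scan.
- A reader might take 1 − 0.7837 = 21.6% as the size of the defect. It is the ordinary chance of at least one response in 8 at a 3% rate and has nothing to do with radiation.
- A reader might infer an inflated Type I error. With the assumed f of 1% to 5%, the chance of passing both Simon stages would rise from 0.032 to between 0.063 and 0.261. But f has no source, and SAP 10.1.3 says the Simon design will not be performed.

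**Conclusion.** The gap is real but limited. As written, SAP 7.2.2 and 7.2.4 let target-lesion shrinkage after permitted on-study radiotherapy count toward the study drugs, and the primary Part 2 ORR lacks the cut-off that PFS and DOR have for new anticancer treatment. The main exposure is radiotherapy to a target lesion; the new-therapy part is largely handled by conduct. The number affected is unknown and probably small. The consequence falls on a reported ORR and its confidence interval, not on a stop or go decision. The conclusion assumes that subjects irradiated under the exception continue on study and are scanned, and that no rule in the unseen part of Protocol 7.6.1 already makes such lesions non-evaluable. On those terms it is a worthwhile clarification of the primary analysis, not a flaw in the design.

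**What to change.** - **SAP 7.2.2:** count CR, PR and best overall response only from assessments on or before the earliest of first PD, start of new anticancer therapy, and on-study radiotherapy to a target lesion. If the eCRF cannot link radiation to a target lesion, use radiotherapy to any non-brain tumor lesion. Keep these subjects in the ORR denominator.
- **SAP 7.2.4:** apply the same cut-off to best percent change.
- **SAP Table 12:** state whether such radiotherapy counts as new anticancer treatment, so that ORR, DOR and PFS use one rule.

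**Cost.** A few sentences and a date filter. Protocol 5.6 and 7.4 already require concomitant treatments and procedures to be recorded; neither shows that radiation is tied to a lesion identifier, hence the fallback. ORR can only stay the same or fall slightly, because a genuine drug response first seen after radiation would no longer count. Sample size, conduct and patient care are unchanged.
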